6.2.4.4. Guidelines for Treatment with Corticosteroids

If in the opinion of the Investigator/treating physician the exacerbation is severe enough to warrant the need for oral or systemic corticosteroids (with or without antibiotics) the following guidelines should be used.

- The duration of treatment with oral/systemic corticosteroids should be \leq 14 days (dose and type according to local practice)
- The duration of treatment with oral/systemic corticosteroids should not exceed 14 days unless approval is given by the sponsor or representative
- Any course of oral/systemic corticosteroids started within 7 days of finishing a previous course will be considered as treatment for a single exacerbation

6.2.4.5. Guidelines for Treatment with Antibiotics

If there is evidence of respiratory infection that in the opinion of the Investigator or treating physician warrants the need for antibiotics the following guidelines should be followed:

- The duration of treatment with antibiotics should be 7 to 14 days (dose and type according to local practice). If first line antibiotic treatment fails and additional antibiotics are used, the total duration of antibiotic treatment should not exceed 30 days unless approval is given by the sponsor or representative
- Any course of antibiotics started within 7 days of finishing a previous course will be considered as treatment for a single exacerbation

Use of antibiotics for the treatment of upper or lower respiratory tract infections is not considered a COPD exacerbation unless the subject experiences worsening of symptoms of COPD as described in Section [6.2.4.1](#).

6.2.4.6. Onset and Resolution of COPD Exacerbations

For each mild, moderate and severe exacerbation, the date of onset and the date of resolution will be recorded in the study source documents and eCRF.

The date of onset is the first day (of at least 2 consecutive days) of worsening symptoms of COPD as described in Section [6.2.4.1](#).

The date of resolution should be based on when the Investigator and/or subject determines that the COPD symptoms have returned to pre-exacerbation levels or to a new baseline. In determining this resolution date, consideration should be given to diary recorded symptoms and/or study subject evaluation.

6.2.4.7. Guideline for assessing multiple mild exacerbations

Two mild exacerbations can be combined into one, per the Investigator's judgement, if a subject's diary reveals that the two mild COPD exacerbations are separated by no more than three exacerbation free days.

6.2.4.8. Guideline for assessing exacerbations that increase in severity

If an exacerbation starts off as mild, but becomes moderate or severe or starts off as moderate and becomes severe, the exacerbation should be captured as one exacerbation and classified by its highest level of severity.

6.2.5. Spirometry Testing

Spirometry measurements will be obtained using spirometry equipment that meets or exceeds the minimal performance recommendations of the ATS [[Miller, 2005](#)]. All subjects will have spirometry performed at Screening and each scheduled clinic visit during the treatment period. At the screening visit both pre- and post-albuterol/salbutamol spirometry measurements will be measured in order to assess eligibility and reversibility (see Section [6.2.5.1](#)). At Visits 2-7 (and discontinuation of IP

visit) both pre- and post-albuterol/salbutamol spirometry will be measured prior to the subject taking their morning dose of IP. For FEV₁ and FVC determinations, at least 3 acceptable spirometry efforts (with no more than 8) should be obtained. Acceptable spirometry efforts should have a satisfactory start of test and end of test (*e.g.* a plateau in the volume-time curve) and be free from artifacts due to cough, early termination, poor effort, obstructed mouthpiece, equipment malfunction, or other reasons [Miller, 2005].

The largest FEV₁ and FVC from the 3 acceptable efforts should be recorded, even if they do not come from the same effort.

Spirometry must be performed as follows:

- Started approximately between 6:00AM and 11:00AM.
- If applicable, after completing the health outcomes assessments (SGRQ-C, BDI/TDI, EQ5D, CAT, Activity limitation, HRU, COPD assessment).
- After withholding albuterol/salbutamol for ≥ 4 hours.
- At screening, before the morning dose of their usual COPD medications.
- At randomization and all treatment visits, before the morning dose of IP.
- Subjects should refrain from smoking for 1 hour prior to each pulmonary function test.
- Subjects should abstain from drinking beverages with high levels of caffeine such as tea and coffee for 2 hours prior to each pulmonary function test.

A full description of the timing and conduct of spirometry procedures is provided in the SPM.

6.2.5.1. Reversibility Testing

At Visit 1, both pre- and post-albuterol/salbutamol spirometry will be obtained. Post-albuterol/salbutamol FEV₁ and FEV₁/FVC findings will be used to determine subject eligibility.

Reversibility testing will be completed as follows: Following pre-albuterol/salbutamol spirometry (three acceptable spirometry efforts), the subject will self-administer 4 puffs of albuterol/salbutamol MDI using a spacer/valved-holding chamber. Three acceptable spirometry efforts will be obtained approximately 10 to 30 minutes after albuterol/salbutamol administration.

6.2.6. SGRQ-C

The St George's Respiratory Questionnaire -COPD specific (SGRQ-C) will be completed by subjects at Randomization, at Week 4, Week 28 and Week 52 (or at the IP Discontinuation Visit).

The SGRQ-C [Meguro, 2007] is a disease-specific questionnaire designed to measure the impact of respiratory disease and its treatment on a COPD patient's HRQoL. As well as producing an overall summary score, scores for the individual domains of symptoms,

activity and impacts are also produced. It has been used in studies of COPD subjects and has been translated and validated for use in most major languages. The SGRQ-C is derived from the original SGRQ, and produces SGRQ scores equivalent to the SGRQ instrument [Meguro, 2007].

6.2.7. Diary Assessments

Subjects will complete a daily eDiary to provide the following information:

- Number of nighttime awakenings due to COPD symptoms
- Use of supplemental albuterol/salbutamol
- Major symptoms concerning the subject's dyspnea, sputum volume, sputum purulence (color)
- Minor symptoms of cough, wheezing, sore throat, colds (nasal discharge and/or nasal congestion), fever without other cause
- Subjects will also be asked 'Did your respiratory symptoms stop you performing your usual activities in the last 24 hours?' with a Yes/No answer.

Subjects will be instructed to complete the daily eDiary in the morning, prior to taking any IP medication. Subjects will be instructed on how to use the eDiary to score each of these major and minor symptoms daily. COPD exacerbations will be identified based on eDiary review, and Investigator judgment. In addition, subjects will also capture their use of albuterol/salbutamol, the number of nighttime awakenings and if their activity level was affected by their respiratory symptoms.

Investigator judgment should be used in deciding whether to report the signs and symptoms (and/or determine diagnosis) as recorded in the diary as an AE/SAE in the eCRF. Refer to Section 6.3.2.1 and Section 6.3.2.2 for definitions of AE and SAE, respectively.

6.2.8. Rescue Albuterol/Salbutamol Use

Study supplied albuterol/salbutamol MDI and/or Nebules for use as rescue medication throughout the study will be sourced by GSK for centers in the United States of America; for all other centers it will be sourced locally where possible. Subjects will be instructed to record via daily eDiary the number of occasions rescue albuterol/salbutamol was used in the past 24 hours for the relief of COPD symptoms.

6.2.9. Baseline Dyspnoea Index/Transitional Dyspnoea Index

The BDI is used to measure the severity of dyspnoea in patients at baseline. The TDI measures changes in the patient's dyspnoea from baseline. The scores in both indexes depend on ratings for three different categories: functional impairment; magnitude of task; and magnitude of effort. The BDI will be measured at randomisation. TDI will be measured at Week 4, Week 28 and Week 52 (or IP Discontinuation Visit). Data will be collected in a subset of subjects at selected sites where translations are available.

6.2.10. COPD Assessment Test (CAT)

The CAT will be completed by subjects at screening, randomization, Week 4, Week 28 and Week 52 (or IP Discontinuation Visit).

The COPD Assessment Test (Jones, 2009; Jones, 2012) is a validated, short and simple patient completed questionnaire which has been developed for use in routine clinical practice to measure the health status of patients with COPD. The CAT is an 8-item questionnaire suitable for completion by all patients diagnosed with COPD. When completing the questionnaire, subjects rate their experience on a 6-point scale, ranging from 0 (no impairment) to 5 (maximum impairment) with a scoring range of 0-40. Higher scores indicate greater disease impact.

6.2.11. Subject Global Rating of Activity Limitation and Subject Global Impression of Change in Activity Limitation

Subjects will complete the Global Rating of Activity Limitation at randomisation and all subsequent visits including the final visit (or IP Discontinuation Visit). This single global question will ask subjects to rate their activity limitation on a four-point scale (not limited, slightly limited, limited, very limited).

Subjects will complete a Global Impression of Change in Activity Limitation question at all visits subsequent to randomisation including the final visit (or IP Discontinuation Visit). Response options will be on a 7 point Likert scale ranging from much better to much worse.

(Note: The above assessments are in addition to the subject's daily diary recording of activity level that was affected by their respiratory symptoms.)

6.2.12. Subject Global Rating Severity of COPD and Subject Global Impression of Change in COPD

Subjects will complete the Global rating severity of COPD at randomization. This single global question will ask subjects to rate their severity of COPD on a four point scale (mild, moderate, severe, very severe).

Subjects will complete a Global Rating of Change in COPD (overall disease) question at all visits subsequent to randomisation including the final visit (or IP Discontinuation Visit). Response options will be on a 7 point Likert scale ranging from much better to much worse. Asking at each visit allows for early detection of response as well as continued response.

6.3. Safety

See Section 9.8 and Section 9.9 for information on IDMC and adjudication of SAEs.

Safety endpoints and other assessments

- Incidence of adverse events

- Incidence of pneumonia
- Incidence of cardiovascular events (including supraventricular arrhythmia and non fatal myocardial infarction)
- ECG measurements
- Vital signs
- Hematological and clinical chemistry parameters
- Oropharyngeal examinations
- Incidence of bone fractures
- Radiography (CXR)
- Physical examinations
- Pulse oximetry
- Urine pregnancy test (for women of child-bearing potential)

6.3.1. Liver chemistry stopping and follow up criteria

Phase III-IV liver chemistry stopping and follow up criteria have been designed to assure subject safety and evaluate liver event etiology (in alignment with the FDA premarketing clinical liver safety guidance).

Phase III-IV liver chemistry stopping criteria 1-5 are defined below and are presented in a figure in [Appendix 3](#):

1. ALT \geq 3xULN and bilirubin \geq 2xULN (>35% direct bilirubin) (or ALT \geq 3xULN and INR>1.5, if INR measured)

NOTE: if serum bilirubin fractionation is not immediately available, discontinue study drug for that subject if ALT \geq 3xULN and bilirubin \geq 2xULN. Serum bilirubin fractionation should be performed if testing is available. If testing is unavailable, **record presence of detectable urinary bilirubin on dipstick**, indicating direct bilirubin elevations and suggesting liver injury.

2. ALT \geq 8xULN.
3. ALT \geq 5xULN but <8 xULN persists for \geq 2 weeks
4. ALT \geq 3xULN if associated with symptoms (new or worsening) believed to be related to hepatitis (such as fatigue, nausea, vomiting, right upper quadrant pain or tenderness, or jaundice) or hypersensitivity (such as fever, rash or eosinophilia).
5. ALT \geq 5xULN but <8 xULN and cannot be monitored weekly for \geq 2 weeks

When any of the liver chemistry stopping criteria 1-5 is met, do the following:

- **Immediately** discontinue investigational product for that subject
- Report the event to GSK **within 24 hours** of learning its occurrence

- Complete the liver event CRF and SAE data collection tool if the event also meets the criteria for an SAE. All events of ALT \geq 3xULN **and** bilirubin \geq 2xULN (>35% direct) (or ALT \geq 3xULN **and** INR>1.5, if INR measured); INR measurement is not required and the threshold value stated will not apply to patients receiving anticoagulants), termed ‘Hy’s Law’, **must be reported as an SAE (excluding studies of hepatic impairment or cirrhosis).**

NOTE: if serum bilirubin fractionation is not immediately available, discontinue IP for that subject if ALT \geq 3xULN **and** bilirubin \geq 2xULN. Serum bilirubin fractionation should be performed if testing is available. If testing is unavailable, **record presence of detectable urinary bilirubin on dipstick**, indicating direct bilirubin elevations and suggesting liver injury.

- Complete the liver imaging and/or liver biopsy CRFs if these tests are performed
- Perform liver event follow up assessments, and monitor the subject until liver chemistries resolve, stabilise, or return to baseline values as described below.
- Discontinue investigational product after completion of the liver chemistry monitoring as described below.
- Do not restart investigational product.

In addition, for criterion 1:

- Make every reasonable attempt to have subjects return to clinic within **24 hours** for repeat liver chemistries, liver event follow up assessments (see below), and close monitoring
- A specialist or hepatology consultation is recommended
- Monitor subjects twice weekly until liver chemistries (ALT, AST, alkaline phosphatase, bilirubin) resolve, stabilise or return to within baseline values

For criteria 2, 3, 4 and 5:

- Make every reasonable attempt to have subjects return to clinic **within 24-72 hrs** for repeat liver chemistries and liver event follow up assessments (see below)
- Monitor subjects weekly until liver chemistries (ALT, AST, alkaline phosphatase, bilirubin) resolve, stabilise or return to within baseline values; criterion 5 subjects should be monitored as frequently as possible.

Subjects with ALT \geq 5xULN and <8xULN which exhibit a decrease to ALT \geq 3xULN, but <5xULN and bilirubin <2xULN without hepatitis symptoms or rash, and who can be monitored weekly for 4 weeks:

- Notify the GSK medical monitor within 24 hours of learning of the abnormality to discuss subject safety
- Can continue investigational product

- Must return weekly for repeat liver chemistries (ALT, AST, alkaline phosphatase, bilirubin) until they resolve, stabilise or return to within baseline
- If at any time these subjects meet the liver chemistry stopping criteria, proceed as described above
- If, after 4 weeks of monitoring, ALT <3xULN and bilirubin < 2xULN, monitor subjects twice monthly until liver chemistries normalise or return to within baseline values.

For criteria 1-5, make every attempt to carry out the **liver event follow up assessments** described below:

- Viral hepatitis serology including:
 - Hepatitis A IgM antibody;
 - Hepatitis B surface antigen and Hepatitis B Core Antibody (IgM);
 - Hepatitis C RNA;
 - Cytomegalovirus IgM antibody;
 - Epstein-Barr viral capsid antigen IgM antibody (or if unavailable, obtain heterophile antibody or monospot testing);
 - Hepatitis E IgM antibody
- Blood sample for PK analysis, obtained within 72 hours of last dose. Record the date/time of the PK blood sample draw and the date/time of the last dose of investigational product prior to blood sample draw on the CRF. If the date or time of the last dose is unclear, provide the subject's best approximation. If the date/time of the last dose cannot be approximated OR a PK sample cannot be collected in the time period indicated above, do not obtain a PK sample. Instructions for sample handling and shipping are in the SPM.
- Serum creatine phosphokinase (CPK) and lactate dehydrogenase (LDH).
- Fractionate bilirubin, if total bilirubin $\geq 2xULN$.
- Obtain complete blood count with differential to assess eosinophilia.
- Record the appearance or worsening of clinical symptoms of hepatitis or hypersensitivity, such as fatigue, nausea, vomiting, right upper quadrant pain or tenderness, fever rash or eosinophilia as relevant on the AE report form.
- Record use of concomitant medications, acetaminophen, herbal remedies, other over the counter medications, or putative hepatotoxins, on the concomitant medications report form.
- Record alcohol use on the liver event alcohol intake case report form.

The following are required for subjects with ALT $\geq 3xULN$ and bilirubin $\geq 2xULN$ (>35% direct) but are optional for other abnormal liver chemistries:

- Anti-nuclear antibody, anti-smooth muscle antibody, and Type 1 anti-liver kidney microsomal antibodies and quantitative total immunoglobulin G (IgG or gamma globulins).
- Serum acetaminophen adduct HPLC assay (quantifies potential acetaminophen contribution to liver injury in subjects with definite or likely acetaminophen use in the preceding week [[James, 2009](#)]). **NOTE: not required in China.**
- Only in those with underlying chronic hepatitis B at study entry (identified by positive hepatitis B surface antigen): quantitative hepatitis B DNA and hepatitis delta antibody. **NOTE:** if hepatitis delta antibody assay cannot be performed,, it can be replaced with a PCR of hepatitis D RNA virus (where needed) [[Le Gal, 2005](#)].
- Liver imaging (ultrasound, magnetic resonance, or computerised tomography) to evaluate liver disease.

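### Section 6.3.1 tells sites to stop study drug at once when a liver stopping criterion is met, and also to stop it only after liver monitoring ends; the second instruction should be deleted

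*Protocol*

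**What the plan says.** Protocol Section 6.3.1 defines five liver stopping criteria and then gives a single list of actions under the heading "When any of the liver chemistry stopping criteria 1-5 is met, do the following". On IP, that list contains:

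- a first bullet that opens with a bold Immediately and continues "discontinue investigational product for that subject";
- a bullet on follow-up assessments that tells the site to "monitor the subject until liver chemistries resolve, stabilise, or return to baseline values as described below";
- directly after it, "Discontinue investigational product after completion of the liver chemistry monitoring as described below";
- directly after that, "Do not restart investigational product".

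The note to criterion 1 reads "NOTE: if serum bilirubin fractionation is not immediately available, discontinue study drug for that subject" when ALT and total bilirubin are over their limits. The note is repeated, in nearly the same words, inside the action list.

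A separate paragraph covers subjects whose ALT was 5 to <8xULN and has fallen to 3 to <5xULN, with bilirubin <2xULN, no hepatitis symptoms or rash, and weekly monitoring possible for 4 weeks. For them the instruction is "Can continue investigational product", with the proviso "If at any time these subjects meet the liver chemistry stopping criteria, proceed as described above".

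Section 4.4.1 makes permanent discontinuation of IP mandatory when a liver criterion is met. It refers to Section 6.3.1 for the criteria and does not say when the drug must stop.

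**The concern.** The same list gives two times for the same act. One is the moment the criterion is met. The other is the end of a monitoring period that has no fixed length. Section 4.4.1 does not settle the timing, so Section 6.3.1 is the controlling text, and it gives two answers.

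The rule protects subjects with possible drug-induced liver injury, and criterion 1 is the Hy's Law case. A site that acted on the later bullet would go on dosing such a subject through twice-weekly checks (criterion 1) or weekly checks (criteria 2 to 5) until the values settled.

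Some general text could make a delay look normal. Section 3.1 encourages subjects who wish to stop IP to keep taking it until the IP Discontinuation Visit. Section 5.1 has the last dose taken in clinic at that visit, and Table 4 marks in-clinic IP administration there. None of this was written for liver stops.

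**Working it through.** No sample size, power or error rate is involved. The check is whether any reading lets both bullets stand.

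1. **Can both be carried out in sequence?** No. Once IP has been stopped at once and may not be restarted, nothing remains to discontinue when monitoring ends.

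2. **Could the later bullet belong to another group of subjects?** Not on the visible text. It sits inside the list for criteria 1 to 5, before the group that may stay on IP is introduced. That group has its own bullets and is sent back to the list above if it meets a stopping criterion. Criteria 3 and 5 imply that a subject at 5 to <8xULN who can be monitored weekly may stay on IP for up to 2 weeks, but that subject has not yet met a criterion, so the list does not apply.

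3. **Does the later bullet carry a duty found nowhere else?** No. The bullet before it and the criterion-specific bullets already set the monitoring and its frequency. It is not needed as a study-exit rule either: Section 4.4 says that stopping IP does not require leaving the study, and Section 4.5 sets no protocol-specific withdrawal criteria.

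4. **Which timing is intended?** Immediate stopping. The word is in bold, the criterion 1 note requires a stop even before fractionated bilirubin is available, and restarting is forbidden. The recall times (24 hours for criterion 1, 24 to 72 hours for the others) and the PK sample within 72 hours of the last dose are consistent with this, though they would not decide it alone.

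5. **Is the bullet superseded text?** No. The amendment log in Appendix 5 records no change to it.

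6. **When could it prolong dosing?** Section 6.3.12 schedules on-treatment chemistry at Weeks 16, 28 and 52, which is 3 draws. Dosing ends at Week 52, so 3 − 1 = 2 scheduled draws (Weeks 16 and 28) could be followed by prolonged dosing. Unscheduled safety draws add to this. No count of extra doses can be given, because the protocol states no monitoring duration.

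**The case against.** The strongest reply is that the error is unlikely to do harm. A site working down the list has already stopped IP when it reaches the disputed bullet, which then has nothing to act on. To be misled, the site would have to disregard the bold first bullet, both bilirubin notes, the ban on restarting, the mandatory discontinuation in Section 4.4.1, the 24-hour report, and the sponsor contact at onset of elevations that Section 6.3.11 requires. This stands as a limit on the likely harm. It does not make the text right, and Section 4.4.1 gives no timing that would resolve the conflict.

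A second reply is that the documents do not show how the bullet arose. It may have been meant to say when a subject can leave the study after monitoring, in which case rewording would serve as well as deletion. The origin is indeed unknown, but the protocol needs no such rule (step 3 above), so deletion loses nothing.

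A third is that the Appendix 3 algorithm figure is not available here. The conclusion therefore rests on the text. A figure could confirm which timing applies, but it could not make both bullets possible to follow.

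**Conclusion.** The concern holds. Section 6.3.1 contains two incompatible instructions on when to stop IP for all five liver criteria, and the later one is wrong as written. The practical effect is probably small. That few subjects would be affected is an assumption, since the documents give no incidence of liver stopping events. Because this is a stopping rule for possible drug-induced liver injury, to be applied at about 1,200 centers, the correction should be made. It has no bearing on the efficacy analysis, the type I error or the power.

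**What to change.** Delete the later bullet in Section 6.3.1, with no replacement. Leave the immediate-stop bullet, the monitoring bullets and the no-restart bullet as they are. The list then reads: stop IP at once, report within 24 hours, complete the forms, assess and monitor, do not restart.

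An optional clarification is a Table 4 footnote to the in-clinic IP row, saying that no IP is given at the IP Discontinuation Visit to a subject already stopped under the liver criteria. The statement that the last dose is taken at that visit also appears in the Protocol Summary and in Sections 3.1 and 5.1, so the footnote should say that it overrides those places.

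The edit is one deleted bullet plus, if wanted, one footnote. It adds no procedure and changes nothing in follow-up, analysis or sample size. Section 9.2 requires ethics review of amendments, so the sensible route is to include the edit in the next amendment and send sites a short clarification in the meantime.
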